8.1.3.2 Exploratory Efficacy Endpoint(s)

There are no exploratory efficacy endpoints in this study.

8.1.3.3 Exploratory Immunogenicity Endpoint(s)

The exploratory endpoints determined by the MN assay against homologous strains at Days 1 and 22, include the following:

- Geometric mean titer (GMT).
- Geometric mean ratio calculated at Day 22/Day 1.
- Percentage of subjects with a four-fold rise in MN antibody titer at Day 22
- Reverse cumulative distributions of MN titers at Day 22.
- Additionally, an estimate of the serologic correlate of protection on the basis of HI or other immunological responses including MN, measured three weeks after vaccination against the respective strain.

Further details regarding the statistical approach to estimate potential immunologic correlates of protection are further described in [section 8.4.4.3](#).

8.2 Success Criteria

The study is considered successful if the primary efficacy objective is achieved together with an acceptable safety profile for aQIV vaccine.

8.2.1 Success Criteria for Primary Objective(s)

8.2.1.1 Success Criteria for Primary Safety Objective(s)

Not applicable.

8.2.1.2 Success Criteria for Primary Efficacy Objective(s)

The primary efficacy objective is achieved if the lower-limit (LL) of the two-sided 95% CI of absolute vaccine efficacy estimate is > 0.4 using the primary protocol definition of ILI. In case more than one interim analysis is necessary the type 1 error (alpha) and hence the confidence level of the interval will be adjusted.

8.2.1.3 Success Criteria for Primary Immunogenicity Objective(s)

Not applicable.

8.2.2 Success Criteria for Secondary Objective(s)

8.2.2.1 Success Criteria for Secondary Safety Objective(s)

Not applicable.

8.2.2.2 Success Criteria for Secondary Efficacy Objective(s)

The key secondary objective is achieved if the lower-limit (LL) of the two-sided 95% CI of absolute vaccine efficacy estimate is > 0.4 . As for the primary efficacy objective, the CI confidence level will be adjusted to reflect adjustment of type 1 error (alpha) in case of more than one interim analysis.

Other secondary efficacy/effectiveness objectives will not be tested for success.

8.2.2.3 Success Criteria for Secondary Immunogenicity Objective

The endpoints of percent of subjects achieving seroconversion and HI titer $\geq 1:40$ at Day 22 will be assessed against the criteria described in CBER Guidance Clinical Data Needed to Support the Licensure of Seasonal Inactivated Influenza Vaccines (2007):

- The lower bound of the two-sided 95% CI for the percentage of subjects achieving seroconversion for HI antibody should meet or exceed 30%.
- The lower bound of the two-sided 95% CI for the percentage of subjects achieving an HI antibody titer $\geq 1:40$ should meet or exceed 60%.

8.3 Analysis Sets

8.3.1 All Enrolled Set

All screened subjects who provide informed consent, received subject ID and provided demographic and/or baseline screening assessments, regardless of the subject's randomization and treatment status in the study.

8.3.2 All Exposed Set

All subjects in the enrolled set who receive a study vaccination.

8.3.3 Safety Set

Solicited Safety Set (solicited local and systemic adverse events and other solicited adverse events)

A randomly selected sample of 1053 subjects from each treatment arm of the Exposed Set with any solicited adverse event data, indicating the occurrence or lack of occurrence of solicited adverse events (e.g., use of analgesics/antipyretics medication).

Unsolicited Safety Set (unsolicited adverse events)

All subjects in the Exposed Set with unsolicited adverse event data, indicating the occurrence or lack of occurrence of an adverse event.

Overall Safety Set

All subjects who are in the Solicited Safety Set and/or Unsolicited Safety Set.

Subjects will be analyzed as “treated” (i.e., according to the vaccine a subject received, rather than the vaccine to which the subject may have been randomized).

Subjects with reportable stratification errors will be analyzed “as corrected”, (i.e. analyze subject in corrected stratum) in safety. Subjects with non-reportable stratification errors will be shifted and analyzed in their correct stratum in safety.

8.3.4 Full Analysis Set (FAS) Efficacy/Immunogenicity Set

Full Analysis Set Efficacy (primary and secondary efficacy objectives)

All subjects in the All Enrolled Set who are randomized and receive a study vaccination, are under observation for at least 21 days post-vaccination and provide efficacy data.

Full Analysis Set Immunogenicity

A randomly selected sample of 1,702 subjects including subjects from both treatment arms (1,362 aQIV; 340 Boostrix), in the All Enroled Set who are randomized, receive a study vaccination and provide blood specimens before and after vaccination. Several FASs for all relevant immunogenicity endpoints will be detailed in the SAP.

8.3.5 Per Protocol (PP) Set Efficacy/Immunogenicity Set

All subjects in the FAS Efficacy / Immunogenicity who:

- Correctly receive the vaccine (i.e., receive the vaccine to which the subjects is randomized and at the scheduled time points).
- Have no protocol deviations leading to exclusion (see [Section 8.3.7, Protocol Deviations](#)) as defined prior to unblinding / analysis.
- Are not excluded due to other reasons defined prior to unblinding or analysis (see [Section 8.3.7, Protocol Deviations](#)).

PPS are subsets of FAS and should be always defined even if the objectives do not require it.

Examples for subjects excluded due to other reasons than protocol deviations are subjects who withdrew informed consent.

In case of misrandomization with regard to treatment arm, the subject is excluded from the PPS. If a subject receives a vaccine, labelled for another subject but the same as the one the subject was randomized to, the subject will not be removed from the PPS.

If a subject received the correct study vaccine (dose, batch) but from another ongoing study at the site then the subject should be excluded from the PPS.

Subjects with reportable stratification error will be excluded from the PPS. A stratification error is considered “reportable” when it has a major impact to the vaccination dose and/or to the vaccination schedule of a subject.

Subjects with non-reportable stratification errors will be analyzed in the correct stratum in PPS.

If a subject is unblinded during the study, except for SUSAR, or AESI he/she will be excluded from the PPS.

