8.3.7 Protocol Deviations

A protocol deviation is any change, divergence, or departure from the study design or procedures of a study protocol. A protocol deviation may be a reason to remove data from an analysis set at the time of analysis. CSR-reportable protocol deviations as well as exclusion actions taken will be specified in the SAP. In some cases exclusion of data may be due to a reason other than a protocol deviation, e.g. early termination.

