8.4.2.2.2 Analysis Sets

Primary vaccine efficacy analyses will be based on the Efficacy FAS, and repeated on the Efficacy PPS.

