6. DETERMINATION OF PROTOCOL DEVIATIONS

6.1 Definition of Protocol Deviations

CSR reportable PD are defined in accordance with International Conference on Harmonization (ICH) E3 as important PDs related to study inclusion or exclusion criteria, conduct of the trial, subject management or subject assessment resulting in the potential to jeopardize the safety or rights of the trial subjects or the scientific value of the trial. Protocol deviations will be classified as CSR-reportable and non-CSR-reportable and a pre-specified list of protocol deviations will be included in the Protocol Deviation Specification document included in appendix A of this Statistical Analysis Plan.

All reportable PDs will be evaluated before unblinding and most will be classified into the following categories:

- Subject randomized and did not satisfy entry criteria
- Subject developed withdrawal criteria during the study, but was not withdrawn
- Subject received the wrong treatment or incorrect dose
- Subject took an excluded concomitant medication
- Key study procedures missed or performed out of window

CSR reportable PDs will lead to exclusion of the subject or part of the subject's data from at least one analysis set.

The number of subjects in any and by PD category will be summarized by study group and overall. Individual subject listings will be provided in an appendix, sorted by subject and by PD category.

Prior to unblinding, designated study staff will develop a memo that describes the PDs that led to exclusions from analysis sets. This memo will be signed off by at least the Biostatistician and the Clinical Program Medical or Scientific Lead (CPML/CPSL) and will be included in the trial master file.

Prematurely terminating study participation for reasons such as withdrawal of consent or occurrence of adverse events (including death) is not considered as a PD. The missing assessments that should have otherwise been collected for that subject later in the study are also not considered as a PD.

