6.2 Determination of Protocol Deviations

A set of listings will be provided to the Clinical Program Medical or Scientific Lead and the Global Clinical Operations Lead for review on an ongoing basis during the study.

The listings will be programmed following the Protocol Deviation Specification list presented in table in [section 7.7](#).

The review will also include protocol deviations captured reported in monitoring reports.

After the review, the Clinical Program Medical or Scientific Lead and the Global Clinical Operation Lead will provide the Biostatistician with:

- An assessment of CSR reportable PDs based on blinded clinical data review.
- An assessment of subjects without PDs (e.g., premature withdrawals due to adverse event, withdrawal of consent) who should be excluded from an analysis set.

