7.4 Per Protocol Set (PPS)

All subjects in the FAS Efficacy / Immunogenicity who:

- Correctly received the vaccine (i.e., receive the vaccine to which the subjects is randomized to receive).

- Had no CSR-reportable PD leading to exclusion (see [section 6.2](#)) as defined prior to unblinding or analysis.
- Are not excluded due to other reasons defined prior to unblinding (see [section 6.2](#))

In case of vaccination error, the subject is excluded from the PPS. If a subject receives a vaccine, labelled for another subject but the same as the one the subject was randomized to, the subject will not be removed from the PPS.

If a subject received the correct study vaccine (dose, batch) but from another ongoing study at the site, then the subject should be excluded from the PPS.

See [section 4.1](#) for details on how to handle subjects randomized in the wrong stratum.

If a subject is unblinded during the study (except for possible SUSARs), he/she will be excluded from the PPS.

Primary vaccine efficacy analyses will be based on the Efficacy/immunogenicity FAS, and repeated, as a sensitivity analysis, on the Efficacy/immunogenicity PPS.

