12. EFFICACY ANALYSIS

12.1 Primary Objectives Analysis

The primary absolute efficacy objective will be evaluated using following null (H_0) and alternative (H_1) hypotheses:

$$H_0: 1 - HR = VE \leq 0.4 \quad \text{versus} \quad H_1: 1 - HR = VE > 0.4,$$

where HR is a hazard ratio of aQIV versus non-influenza comparator and VE is vaccine efficacy. The primary objective will be demonstrated if the lower limit of the two-sided confidence interval of VE estimate, with at least 95% coverage in a multiple sequential hypothesis testing, exceeds 40%. In case an interim analysis is performed, the 95% CI will be adjusted accordingly. If an interim analysis is performed and the trial doesn't stop, then all the subsequent analysis will be tested at a reduced alpha level, i.e. what's left from the interim analysis. The confidence interval will be higher than 95% instead of 95% for the final analysis.

Primary vaccine efficacy analyses will be based on the Efficacy FAS, and repeated on the Efficacy PPS.

The HR and the related 95% CI of HR, for onset of first RT-PCR confirmed influenza will be estimated by a proportional hazards regression model with treatment effect as a fixed effect and stratifying covariates as a random effect:

$h_i(t|X) = h_0(t) \exp(\beta^T X + b^T Z)$, with t denoting time to the influenza, β is the effect of treatment group indicated by X , b is random effect (assumed as a multivariable random gaussian variable with zero mean and diagonal covariance matrix), Z is random effect covariate (reflecting randomization strata, see [Section 8.1](#) for further discussion of the covariates utilised).

Subjects that did not experience ILI during observation period and subjects that dropped out from the study during observational period will be censored (right-censoring). The estimate of the hazard ratio, the respective estimate for absolute VE and the pertaining 2-sided CIs will be calculated based on this model. If the study continues over several seasons, estimates will be also adjusted for the factor season (s). In case of one or two (interim) analyses, confidence levels at each stage will be adjusted, as discussed in [section 14.1](#), to provide 95% overall coverage.

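### The Efficacy PPS excludes subjects who withdrew consent, and may exclude other early leavers without a stated criterion, although the Cox model already censors drop-outs; membership can turn on events after the endpoint.

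*Protocol*

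**What the plan says.** Protocol 8.3.5 defines the PPS by subject. Besides protocol deviations it allows exclusion for other reasons, and illustrates them: "Examples for subjects excluded due to other reasons than protocol deviations are subjects who withdrew informed consent". It gives no time limit, makes no exception for a subject who already has a confirmed case, and has no rule to censor at withdrawal.

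Three further places bear on it:

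- Protocol 8.3.7, to which 8.3.5 refers for those other reasons, is permissive: "In some cases exclusion of data may be due to a reason other than a protocol deviation, e.g. early termination".
- SAP 7.4 keeps the same route open ("Are not excluded due to other reasons defined prior to unblinding"). It names no reason itself but refers to SAP 6.2, where the study leads are to provide "An assessment of subjects without PDs (e.g., premature withdrawals due to adverse event, withdrawal of consent) who should be excluded from an analysis set". No criterion for that assessment is given.
- SAP 6.1 states: "Prematurely terminating study participation for reasons such as withdrawal of consent or occurrence of adverse events (including death) is not considered as a PD". Early leavers can therefore be removed from the PPS for leaving only through the other-reasons route.

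The efficacy model treats the same people differently. SAP 12.1, like Protocol 8.4.2.2.3, says "subjects that dropped out from the study during observational period will be censored (right-censoring".

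On the role of the set, Protocol 8.4.2.2.2 says "Primary vaccine efficacy analyses will be based on the Efficacy FAS, and repeated on the Efficacy PPS", and SAP 7.4 describes the primary analysis as "repeated, as a sensitivity analysis, on the Efficacy/immunogenicity PPS". The key secondary analysis is also repeated on the PPS (Protocol 8.4.3.2.2, SAP 12.2).

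**The concern.** A per-protocol repeat should show whether departures from the protocol change the answer. Here the treatment is a single injection on Day 1, so a subject who leaves on Day 100 or Day 300 has not departed from the assigned vaccine by leaving. For a time-to-first-event endpoint, the follow-up before leaving is usable, and so is any case that occurred in it. The plan's own model uses both.

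The PPS rule does not follow that logic. The endpoint window closes at Day 180 or the end of the season, whichever is longer; follow-up runs to Day 366, and consent may be withdrawn at any time (Protocol 3.8). Membership can then be decided by something that happens after the endpoint. If that happens, an FAS/PPS difference may reflect who left the study rather than who deviated, which weakens the PPS as a check on the primary result.

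**Working it through.** **1. One subject, two sets.** Take a subject vaccinated as randomised, with RT-PCR-confirmed influenza on Day 60, who withdraws consent on Day 250.

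| | FAS Efficacy | Efficacy PPS |
|---|---|---|
| Entry rule | Randomised, vaccinated, observed at least 21 days, provides efficacy data (Protocol 8.3.4): met | In the FAS, correct vaccine, no excluding deviation: met |
| Effect of Day 250 withdrawal | None | Excluded under 8.3.5 |
| Day 60 case | Counted | Leaves with the subject, on the subject-level wording |

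Subjects who leave before 21 days are already outside the FAS, so the point concerns later withdrawals.

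**2. The plan's own figures.** Inputs from Protocol 8.5: attack rates 3.5% (comparator) and 1.4% (aQIV), 4,860 evaluable per group, VE 60%, margin 40%, one-sided alpha 2.5%.

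- Cases: 4,860 × 0.035 = 170.1 and 4,860 × 0.014 = 68.0, total 238.1. This matches the planned 238.
- Power at 238 events, with hazard ratio relative to the margin 0.40/0.60: 87.9% by the Schoenfeld formula at alpha 0.025, 87.0% at 0.02275. Simulation with the Table 8.6-1 boundaries (0.00625, 0.35022, 0.02275) gives 86.5%, the stated value.

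**3. Baseline precision.** SE(log HR) = √(1/170.1 + 1/68.0) = 0.143. Lower 95% limit of VE = 1 − 0.40 × exp(1.96 × 0.143) = 47.0%. This ignores the interim adjustment of the confidence level, which is adequate for comparing scenarios.

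**4. Equal loss of cases.** Let *a* and *c* be the shares of aQIV and comparator cases removed. Then HR = 0.40 × (1 − *a*)/(1 − *c*), with the SE from the remaining cases. Changes in the number of non-cases are ignored.

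Suppose the planned 10% drop-out is unrelated to influenza and half of it falls after a typical case. The share of observed cases later lost is then 0.05/0.95 = 5.3%. The timing is an assumption; if all 10% fell after the cases, the share would be 10%.

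**5. Unequal loss of cases.** The documents give no figure, so the unequal rows are assumptions only.

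| aQIV / comparator cases lost | Cases left | VE | Lower limit |
|---|---|---|---|
| 0 / 0 | 238 | 60.0% | 47.0% |
| 5.3% / 5.3% | 226 | 60.0% | 46.6% |
| 10% / 10% | 214 | 60.0% | 46.2% |
| 5% / 10% | 218 | 57.8% | 43.5% |
| 10% / 20% | 197 | 55.0% | 39.2% |
| 10% / 5% | 223 | 62.1% | 49.2% |
| 20% / 10% | 207 | 64.4% | 51.6% |

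A second calculation started from all 5,346 randomised per group (262 expected cases, lower limit 47.7%) and also removed 10% of non-cases. Equal 10% loss left 236 cases, VE 60.0% and lower limit 46.9%. Assumed losses of 5%/20% and 20%/5% (aQIV/comparator) gave VE 52.7% and 66.2%. The pattern is the same: equal loss costs precision, and only unequal loss moves VE.

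**The case against.** The strongest reply is that little depends on this. Success rests on the FAS, which keeps these subjects; the PPS repeats are supportive, and the other reasons must be defined before unblinding, which prevents arm-aware selection. All of that stands. Deciding before unblinding does not remove a difference between arms in who withdraws, but no such difference is documented.

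Three stronger readings are tempting, and the documents do not support them.

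- *Everyone who stops early is removed.* Only consent withdrawal is given outright, in Protocol 8.3.5. Protocol 8.3.7 is permissive, speaks of data and does not name the PPS. SAP 6.2 asks for an assessment and does not name the set either. SAP 7.4 lists none of these reasons and reaches them only by cross-reference. The defect there is the missing criterion.
- *Earlier confirmed cases are deleted by rule.* No sentence says so. It follows from excluding the subject, but it is an inference.
- *Influenza drives withdrawal, so the PPS VE is biased.* Protocol 3.8 defines withdrawal of consent as leaving for a non-medical reason and lists adverse event and death separately. A subject who leaves because of influenza should be coded to one of those. The argument therefore applies mainly to adverse-event withdrawals, which SAP 6.2 leaves to judgement. The row falling below 40% needs 20% of comparator cases to be lost, twice the planned all-cause drop-out, and a PPS limit below 40% would not change study success.

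Two uncertainties remain. The consent sentence may be meant for withdrawals that require data to be removed; the text does not say. The Protocol Deviation Specification (SAP Appendix A) is not in the text reviewed and could say more, although SAP 6.1 describes it as a list of deviations, which withdrawals are not.

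**Conclusion.** The point holds as a defect in the definition of a supportive analysis set. Protocol 8.3.5 excludes consent withdrawers as whole subjects, and two other sections permit exclusion of other early leavers without a criterion. The model can use these subjects' data, and their leaving says nothing about adherence to a single Day 1 dose.

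With loss unrelated to arm, the cost is about 5% of cases (238 to 226; lower limit 47.0% to 46.6%), or 10% at most under the planned drop-out (lower limit 46.2%), and no bias. Bias in the PPS VE requires loss of cases to differ by arm; its direction and size cannot be derived from the documents. The FAS primary analysis, its power and study success are unaffected.

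**What to change.** - **Protocol 8.3.5:** delete withdrawal of consent as an example of a reason for exclusion from the Efficacy PPS.
- **Protocol 8.3.7, SAP 6.2 and SAP 7.4:** state that withdrawal of consent, withdrawal for an adverse event, or early termination does not by itself exclude a subject from the Efficacy PPS. Such a subject keeps any RT-PCR- or culture-confirmed case with onset before withdrawal and is otherwise censored at withdrawal, as in the FAS.
- **Exception:** withdrawal of consent that legally requires removal of the data.

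The cost is a few lines of text. No extra data or subjects are needed, and the PPS becomes slightly larger. The wording should be settled before unblinding.

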8.3.6 Subgroups

The primary efficacy analysis will be performed by stratifying for the following subgroups:

- Age at enrolment (≥ 65 -74, ≥ 75 -84, and ≥ 85 years);
- Comorbidity/risk (yes/no defined as assessment score < 50 or ≥ 50 based on scale described in the [Section 5.1.2](#) ([Hak, 2004](#));
- Previous influenza vaccination in the past 5 years (yes/no);
- Smoking status (yes/no);
- Sex;
- Race;
- Country;
- By season, if applicable.

Immunogenicity analysis at Day 22 will be performed by stratifying for the following subgroups:

- Age at enrolment (≥ 65 -74, ≥ 75 -84, and ≥ 85 years);
- Comorbidity/risk (yes/no defined as assessment score < 50 or ≥ 50 based on scale described in the [Section 5.1.2](#) ([Hak, 2004](#));
- Previous influenza vaccination in the past 5 years (yes/no);
- Sex;
- Race;

Safety analysis of any unsolicited adverse events and of any local, any systemic, or any other solicited adverse events (all adverse events combined for each such category) will be performed by stratifying for the following subgroups:

- Age at enrolment (≥ 65 -74, ≥ 75 -84, and ≥ 85 years);
- Sex;
- Race;
- Country

8.3.7 Protocol Deviations

A protocol deviation is any change, divergence, or departure from the study design or procedures of a study protocol. A protocol deviation may be a reason to remove data from an analysis set at the time of analysis. CSR-reportable protocol deviations as well as exclusion actions taken will be specified in the SAP. In some cases exclusion of data may be due to a reason other than a protocol deviation, e.g. early termination.

